Study staff are trained to assess the subject's understanding of pertinent information given to them and whether or not subjects can appreciate the implications of their decision. Study staff will ask the subject to reiterate the study procedures back to them and will ensure that the subject has had substantial time to ask questions about any/all study procedures. Study staff will also assess the subject's understanding of the study with a 5-item written quiz. Subjects who answer all the questions in the correct way will be able to sign the consent form.

8. Non-English Speaking Subjects:

There are no plans to recruit or enroll non-English speaking subjects. There are no provisions in the current protocol to accommodate non-English speaking participants (to translate study documents, assessment battery, informed consent form, or other study material into other languages).

As a limited alternative to the above requirement, will you use the short form for consenting process if you unexpectedly encounter a non-English speaking individual interested in study participation and the translation of the long form is not possible prior to intended enrollment? YES NO

9. Consent Waiver: In certain circumstances, the HIC may grant a waiver of signed consent, or a full waiver of consent, depending on the study.

- Not Requesting any consent waivers
- Requesting a waiver of signed consent:
 - Recruitment/Screening only (if for recruitment, the questions in the box below will apply to recruitment activities only)
 - Entire Study (Note that an information sheet may be required.)

For a waiver of signed consent, address the following:

- Would the signed consent form be the only record linking the subject and the research?
 - YES NO
- Does a breach of confidentiality constitute the principal risk to subjects?
 - YES NO

OR

- Does the research pose greater than minimal risk?
 - YES NO
- Does the research include any activities that would require signed consent in a non-research context?
 - YES NO

SECTION IV: PROTECTION OF RESEARCH SUBJECTS

Confidentiality & Security of Data:

1. *What protected health information (medical information along with the HIPAA identifiers) about subjects will be collected and used for the research?*

CUD subjects who decide to participate in the study will have a medical record at the Connecticut Mental Health Center (CMHC) and at Yale New Haven Hospital (YNHH). If subjects already have a medical record at CMHC or YNHH, some information about their participation in the study will be included here. If they do not have a medical record at CMHC or YNHH, one will be made for their visit. The information that will be entered into this medical record will include: name, date of birth, date of admission to the CNRU, date of experiments at the YNHH HRU, date of discharge from the CNRU, X-ray results if required for MRI eligibility, phone number, address, medical history, individual and family history of psychiatric problems, and substance abuse history. One of the instruments used to assess substance abuse history will include questions pertinent to legal problems.

All subjects will be asked to provide their name, date of birth, address, and phone number which will not be used in analyses or presentation of the results. The exact dates of CNRU admission and discharge (CUD subjects only) and exact dates of experiments and procedures will not be used in presentations; however, these dates may be de-identified data (i.e., using coded, subject-specific random identifiers) and used to calculate the time between procedures for use in analyses. All data from medical/psychiatric interviews, urine drug screen results, blood-draws, self-assessments, PET and MRI scans will be collected in the form of de-identified data (i.e., using coded, subject-specific random identifiers) and will be used in analyses and presentations.

2. *How will the research data be collected, recorded and stored?*

Research data will be collected over the phone, by paper-pencil and/or electronic self-questionnaires, computerized testing, by interviews, by use of the self-administration paradigm, physical examination, and laboratory work. This information will be recorded/transferred in each subject's Case Report Form and on password protected University computer servers that are kept in locked offices. However, coded data lacking personal identifiers (name, social security #, address, phone, medical record number, etc.) will be kept on other research desktop and/or laptop computers. Imaging data is collected during the PET/fMRI scans by trained technologists and is stored on password-protected and encrypted computers with identifying information carefully in compliance with HIPAA regulations.

3. *How will the digital data be stored?*

CD DVD Flash Drive Portable Hard Drive Secured Server
 Laptop Computer Desktop Computer Other

4. *What methods and procedures will be used to safeguard the confidentiality and security of the identifiable study data and the storage media indicated above during and after the subject's participation in the study?*

All staff members that come into contact with the data are fully trained to the current HIPAA regulations and are informed as to the proper use of all data. The only ones who have access to this information are the medical personnel and the research staff at the CNRU or at the YNHH HRU. CUD subjects participating in

research at the CHMC and YHNN HRU will have medical records created for them, if they do not already have such records. The researchers and staff at the CMHC and YHNN/HRU will have access to records of any prior admissions, including the details of those admissions, and some information regarding their participation in this study will be included in those records (e.g., dates of admission/discharge, dates of procedures). All information obtained in this study will be stored in locked cabinets or password protected and encrypted computers and hard drives.

Human subjects enrolled in the study are assigned a subject-specific random identifier. Subject identifiers and the means to link the subject names and codes with the research data are stored in separate locations within the database. Direct identifiers belonging to subjects who withdraw from the study will be stripped from the database. The software of the database limits the ability to connect the random identifier to the actual subject identification information to research team members only. Access to the database is password protected and each research team member is required to have a unique ID and password to gain access to the database. Authorized users employ their netid and authentication is performed using Yale's central authentication server.

PET, MRI and assessment data are identified by subject code number rather than name. Users always access research data through the random identifier only. Screening information will remain identified by name. Procedures to protect this PHI have been described above (see Section I, item 11, Section IV, items 2 and 4). After termination of this 5-year study all identifying information will be discarded, but other research data is kept indefinitely. Paper and electronic data will be destroyed by research assistants and study personnel at Yale University following current procedures from the HIC regarding the de-identification, storage, and destruction of records. Private identifiable information will not appear in any publication or be released to anyone without the individual's written consent.

5. *What will be done with the data when the research is completed? Are there plans to destroy the identifiable data? If yes, describe how, by whom and when identifiers will be destroyed. If no, describe how the data and/or identifiers will be secured.*

In accordance with institutional standards and guidelines, after termination of this study and completion of all analysis and publications, all data and screening information will be anonymized and kept in a secure fashion for the purpose of further analyses indefinitely unless prevailing University or Federal guidelines at the time require a change.

6. *If appropriate, has a Certificate of Confidentiality been obtained?*

We have obtained a Certificate of Confidentiality.

SECTION V: POTENTIAL BENEFITS

Potential Benefits: *Identify any benefits that may be reasonably expected to result from the research, either to the subject(s) or to society at large. (Payment of subjects is not considered a benefit in this context of the risk benefit assessment.)*

Subjects will receive a thorough medical and psychiatric evaluation at no cost to themselves, as well as benefit from the knowledge that their participation in such studies may help individuals with cocaine use disorders in the future. It is possible that CUD subjects will experience less cocaine use during the experimental phase of the study. However, it is made clear to subjects that this potential reduction in drug use is not a desired

outcome for this study. Otherwise, there are no direct benefits to individuals participating in this research. Expanding the current understanding on physiological and biological effects of cocaine use could benefit society in as much as better methods of treatment could be designed.

SECTION VI: RESEARCH ALTERNATIVES AND ECONOMIC CONSIDERATIONS

1. Alternatives: *What other alternatives are available to the study subjects outside of the research?*

As this is not a treatment study, the only alternative is to not participate.

2. Payments for Participation (Economic Considerations): *Describe any payments that will be made to subjects, the amount and schedule of payments, and the conditions for receiving this compensation.*

Subjects will be compensated for their time commitment and inconveniences for completing the study at standard rates offered by researchers in the Yale community:

Procedure	Group ¹	Amount
Screening interviews/exams (i.e., to determine eligibility)	B, C	\$25
Baseline self-reports and cognitive tests	C	\$20
Baseline self-reports, cognitive tests, and any repeat exams	B	\$25
Additional self-reports, cognitive testing, and exams (pilot addendum)	B	\$25
PET scanning		
Arrival and setup (including IV and/or arterial line placement)	B	\$50
Injection of radiotracer and/or scan completion ²	B	\$350
MRI scanning		
Arrival and setup	B, C	\$15
Scan completion (part or whole) ²	B, C	\$65
Task-performance earnings	B, C	up to \$20
Inpatient stay		
Duration of primary study procedures (up to 10 days)	B	\$100
Extended duration for pilot addendum (up to 30 days)	B	\$200
Travel reimbursement ³	B, C	

¹ References corresponding Consent version: B) community-recruited CUD subjects; C) HC subjects.

² In cases of technical failures or early termination (either voluntarily or at the discretion of study staff) once procedures have been initiated, subjects will receive full compensation for that procedure

³ Subjects may be required to provide proof of travel costs to receive reimbursement for travel expenses.

Thus, the total amount of subjects could receive for participating in all relevant study procedures (not including possible travel reimbursements) are:

- *Consent B.* Community- and research- recruited CUD subjects: \$650 + \$725; up to \$1375
- *Consent C.* HC subjects: \$245

* NOTE: Consent Forms A and D were related to prior protocol versions and will no longer be used.

Payments will typically be made via a pre-paid debit card in loadable increments after completing individual study procedures using ePayments via Oncore. The debit cards will be provided by the Bank of America and participants will be informed that their name, address, and telephone number will be shared with the bank to order their debit card. Cards may be mailed to subjects or provided in person.

Reimbursements may also be made in the form of small cash payments (i.e., for the outpatient appointments) or checks.

3. **Costs for Participation (Economic Considerations):** *Clearly describe the subject's costs associated with participation in the research, and the interventions or procedures of the study that will be provided at no cost to subjects.*

Subjects will have no financial responsibilities for any portion of the study.

4. **In Case of Injury:** *This section is required for any research involving more than minimal risk, and for minimal risk research that presents the potential for physical harm (e.g., research involving blood draws).*

a. *Will medical treatment be available if research-related injury occurs?*

In the event that a participant develops any mental or physical problems as a direct result of being in this study, our staff will be available to help evaluate the problem

b. *Where and from whom may treatment be obtained?*

As noted above (see Section I, item 11) trained medical and research staff will be present or available to provide assistance during study procedures. Medical treatment, or assistance in obtaining medical care through information and referral, will be offered to the subjects for any physical injuries that they receive as a result of participating in this research.

c. *Are there any limits to the treatment being provided?*

For most of the study related sessions there will be trained research staff on hand who have been trained in recognizing medical emergencies and how to activate an emergency response. However, in case of injury, only evaluation and referral to trained medical staff will be provided.

d. *Who will pay for this treatment?*

The participant or his/her insurance carrier will be expected to pay the costs of this treatment. The study will not cover treatment expenses. No additional financial compensation for injury or lost wages is available; however the subject does not waive any of their legal rights.

e. *How will the medical treatment be accessed by subjects?*

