HRP-503B – BIOMEDICAL RESEARCH PROTOCOL
(2016-1)

Protocol Title: Investigation of cocaine addiction using mGluR5 PET and fMRI

Principal Investigator: [name].

Version Date: MAR 28 2022

Clinicaltrials.gov Registration #: NCT03471182

SECTION I: RESEARCH PLAN

1. Statement of Purpose:

Cocaine use disorder (CUD) remains a significant public health concern that is resistant to current treatments. Challenges to treating CUD include an imbalance in neurobiological systems that 're-wire' the brain such that appetitive and habitual processes influence maladaptive decision-making and behavior. This research project aims to provide insight into this reorganized circuitry in CUD by investigating neurofunctional systems related to glutamatergic plasticity and functional brain networks during initial (2-5 days) abstinence. To target this potentially critical period of recovery, currently-using and non-treatment-seeking individuals with CUD will complete [¹⁸F]FPEB positron emission tomography (PET) and functional magnetic resonance imaging (fMRI) within days of admission to an inpatient research facility. Healthy comparison (HC) subjects from the community or that have participated in [¹⁸F]FPEB PET as part of other Yale approved protocols (HIC#1101007933, HIC#1111009365, HIC#2000027842/2000020186) will be recruited to participate in the fMRI portion of this study.

Aim 1: To determine the availability of mGluR5 using [¹⁸F]FPEB PET during initial abstinence in individuals with CUD. We hypothesize individuals with CUD, relative to HC, will exhibit concurrently and regionally specific increases (e.g., in the striatum) and decreases (e.g., in the prefrontal cortex) in mGluR5 availability.

Aim 2: To determine patterns of resting-state, response-inhibition, an automaticity related connectivity within and between large-scale functional networks using fMRI during initial abstinence in individuals with CUD. We hypothesize network-based analyses of fMRI will reveal lower frontoparietal and greater limbic network modulation in CUD as compared to HC.

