Summary. CUD is one of the most treatment-resistant addictions, and greater understanding of the functional reorganization and neurobiological risk factors of relapse may improve long-term outcomes. We propose to study mGluR5 (a glutamate receptor linked to neuroplasticity) during initial (2-5 days) abstinence in individuals with CUD to examine brain regions and networks of altered neuroplastic capacity. In addition, investigation of resting-state and task-based functional connectivity using fMRI will help clarify the reorganization of brain circuitry that occurs in CUD. Finally, integration of the two modalities using novel analytic methods will lend unique insight into the relationships between these neurofunctional systems.

4. Research Plan:

a. General design and overview

Twenty experienced, currently-using, non-treatment-seeking and medically healthy individuals with cocaine-use disorder (CUD) will participate in a multi-modal imaging investigation of neurofunctional systems during initial (2-5 days) abstinence. Subjects determined to meet eligibility criteria through phone and in-person screening will be scheduled for admission to the Clinical Neuroscience Research Unit (CNRU), Connecticut Mental Health Center (CMHC) for the duration of their study participation (up to 10 days). Following admission (approximately 2-5 days), subjects will undergo a single [¹⁸F]FPEB PET scan at the Yale PET Center and complete an fMRI scanning session at the Yale Magnetic Resonance Research Center (MRRC). Primary outcome measures will include mGluR5 distribution/availability and activity of functional brain networks. Secondary outcomes will include cocaine administration measures (e.g., amount consumed, inter-response intervals, etc.), cocaine-induced subjective effects (e.g., self-ratings of euphoria, 'high', etc.) for subjects having completed the prior study protocol, and psychometric assessments of impulsivity and compulsivity.

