c. PET imaging of mGluR5 with [¹⁸F]FPEB (CUD and HC subjects)

PET scanning sessions will take place at the Yale University PET Center. Subjects will participate in one [¹⁸F]FPEB scan. However, in situations where a PET scan is not successful following [¹⁸F]FPEB injection (e.g., problems with the PET camera), CUD subjects may be rescheduled to complete an additional PET scan, if possible within the 2-5 day window following inpatient admission. HC subjects will complete [¹⁸F]FPEB PET as part of other Yale approved protocols (HIC#1101007933, HIC#1111009365, HIC#2000027842/2000020186).

The PET scan will be acquired as the subject lies supine on the scanner bed. Venous catheters will be used for intravenous administration of the radiotracer and possibly for additional venous blood sampling. A radial artery catheter may be inserted by an experienced physician before the PET scan to draw arterial blood samples for metabolite analysis and for determination of the fraction of plasma radioactivity unbound to protein. Prior to arterial line placement, the skin will be numbed with a local anesthetic so participants will feel less pain when the catheter is inserted. The goal of the arterial line is to be able to measure absolute physiological functions by mathematically relating the signal (from the PET scanner) to the tracer availability (from the blood). This approach is the gold standard for obtaining quantitative PET data. In some cases, for well-established tracers, methods have been developed and validated that provide comparable results to the gold standard. In those cases, the arterial samples may not be necessary. However, validation of such an approach must be performed in each subject group and for each unique experimental design. In this study, if an arterial line cannot be placed, a second intravenous line may be placed for venous blood sampling.

PET scans will be performed with the Siemens HRRT. An attenuation correction scan is obtained immediately before or after each emission scan. The PET scan will be acquired using bolus or bolus plus constant infusion administration of up to 5 mCi of [¹⁸F]FPEB, followed by up to 120 minutes of dynamic PET data acquisition.

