During HABIT performance, participants are instructed to press a button in response to all Go stimuli (e.g., 'X') and withhold responses to NoGo stimuli (e.g., 'K'). Stimuli are presented onscreen for 250-500ms with random inter-trial intervals in order to optimize the analysis of both Go and NoGo events. Task instructions emphasize speed and accuracy equally. At times during the HABIT, participants will be incentivized for their performance (e.g., \$0.10 for correct Go responses, and/or \$0.25c for successful NoGo inhibition, and/or -\$0.10 for failed NoGo inhibition). Task instructions emphasize speed and accuracy equally. Participants will complete up to six runs of up to 6 minutes each, and may earn up to \$20 for their performance. Actual achieved earnings during the task are expected to be between \$10-20, and no participant will receive less than \$5 for task completion, independent of performance (i.e., for subjects earning less than \$5 on the task, they will receive the \$5 minimum additional compensation).

All scans will be conducted by an MRI technologist, and a member of the research team will accompany the study subject and will stay for the MRI session.

As the PI of this protocol has multiple other HIC approved studies involving neuroimaging, the data from this study may be shared across those protocols. Subjects from this protocol may be recruited for the other protocols run under the PI so their data can be analyzed across studies.

e. Participation timeline

Eligible CUD subjects recruited through the community will complete the study procedures according to the described timeline, including interviews (day 0 and possibly day 1), self-assessments (possibly day 0 and day 1), and PET and MRI scanning (between day 3 and day 10; depending on scanner availability) (with day 0 indicating a non-consecutive screening appointment to occur at some time prior to CNRU admission on day 1). For CUD participants, CNRU admission will be scheduled at least 1 day (and no more than 5 days) prior to PET/MRI scanning. While community-recruited participants are expected to remain on the unit 5-8 days total, rare occurrences in scheduling may require more flexibility and inpatient stays up to 14 days.

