CUD subjects. CUD subjects will be 20 experienced, currently-using, non-treatment-seeking, medically-healthy, adult volunteers meeting criteria for cocaine-use disorder (see inclusion/exclusion criteria below; Section I, item 8).

HC subjects. HC subjects will be 20 medically-healthy, adult volunteers that have participated in an [¹⁸F]FPEB scan as part of another Yale approved protocol (HIC#1101007933, HIC#1111009365, HIC#2000027842/2000020186), or that are recruited from the community (Aim 5). Subjects will be contacted to participate in the fMRI portion of this study, and may be asked to completed additional assessments and screening procedures (see inclusion/exclusion criteria below; Section I, item 8).

7. Subject Classification:

 Children	 Healthy	 Fetal material, placenta, or dead fetus
 Non-English speaking	 Prisoners	 Economically disadvantaged persons
 Decisionally impaired	 Employees	 Pregnant women and/or fetuses
 Yale students	 Females of childbearing potential	

NOTE: Is this research proposal designed to enroll children who are wards of the state as potential subjects?

YES NO

Since cocaine dependence often involves serious financial difficulties, it is also possible that some of our subjects may be economically disadvantaged persons. We will carefully screen all participants to make sure that the potential for improvement in their cocaine addiction is the primary motivation for participation. We may enroll females of childbearing potential. All females will be carefully assessed to ensure the absence of pregnancy both before and during study participation.

8. Inclusion/Exclusion Criteria:Inclusion criteria:*HC and CUD subjects:*

- Age 21 - 60 years
- Provide voluntary, written, informed consent
- Physically healthy by medical history, physical, neurological, ECG, and laboratory examinations

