- *For females:* non-lactating, no longer of child-bearing potential or agreeing to practice effective contraception during the study (e.g., established use of oral, injected or implanted hormonal methods of contraception; placement of an intrauterine device [IUD] or intrauterine system [IUS]; barrier methods: condom or occlusive cap [diaphragm or cervical/vault caps] with spermicidal foam/gel/film/cream/suppository; male partner sterilization; true abstinence when this is in line with the preferred and usual lifestyle of the subject), and a negative serum pregnancy (β -HCG) test

CUD subjects:

- DSM-5 criteria for moderate or severe cocaine-use disorder
- Positive urine toxicology screen for cocaine

CUD subjects (Pilot addendum):

- Successful completion of primary study procedures
- Provide voluntary, written, informed consent to participate in additional procedures

Exclusion criteria:*HC and CUD subjects:*

- Any condition that, in the opinion of investigators, would prevent compliance with the study protocol
- A history of significant medical or neurological illness (e.g., coronary artery disease, significant anemia, seizures)

- Current use of psychotropic and/or potentially psychoactive medications
- Physical or laboratory (β -HCG) evidence of pregnancy
- Meet any additional PET/MR imaging-related exclusion criteria, including:
 - Presence of MRI incompatible implants and other contraindications for MRI (e.g., pacemaker, artificial joints, non-removable body piercings, etc.)
 - Participation in other research studies involving ionizing radiation within one year of the PET scans that would cause the subject to exceed the yearly dose limits for healthy volunteers
 - History of a bleeding disorder or are currently taking anticoagulants (such as Coumadin, Heparin, Pradaxa, Xarelto).
 - Claustrophobia
 - Severe motor problems that prevent the subject from lying still for PET/MR imaging
 - Complaints of chronic pain (e.g., as the result of rheumatoid arthritis)
 - Current, past or anticipated exposure to radiation in the work place

CUD subjects:

- Other moderate or severe drug use disorder (except for tobacco-use disorder)
- < 1 year of cocaine use disorder
- A DSM-5 major psychiatric diagnosis (schizophrenia, bipolar disorder, etc.) unrelated to cocaine

HC subjects:

- Any DSM-5 major psychiatric diagnosis (schizophrenia, bipolar disorder, etc.), except tobacco-use disorder
- Positive drug screen

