9. How will *eligibility* be determined, and by whom?

CUD subjects. Potential community-recruited CUD subjects will be initially phone screened by research staff. As part of this screen, subjects will be asked to provide information on medical and psychiatric history, substance use/abuse history, patterns/routes of cocaine use, and whether they are seeking treatment for their cocaine use or not. Potential subjects who pass this phone screening will be scheduled for an in-person screening, which will be done by the study physician, research nurse and/or research coordinator. As part of this screening, subjects will undergo a process of informed consent, including reading the consent form and reviewing it with a study physician and/or trained research staff member. Subjects will receive an explanation of purpose, procedures, benefits, risks, compensation, and alternatives to the study. They will have time to ask any questions and, if interested in participating, will be asked to sign an approved consent form. After providing informed consent for the study, subjects will undergo a physical exam and an informal interview to assess medical, psychiatric, and substance abuse problems, medications, allergies, patterns/routes of cocaine use, and whether they are actively seeking treatment for their cocaine use. They will also undergo a clinician-administered structured interview (i.e., SCID), blood drawing for basic hematologic, chemistry and liver panels, a urine test to detect cocaine and its metabolites, a serum (β -HCG) pregnancy test (if needed) and an electrocardiogram. Information collected during in person screening visits will be discussed by the study physicians, study nurse, research coordinator, and Principal Investigator (who meet on a weekly basis) in order to determine eligibility. CUD subjects recruited through ongoing Cocaine Research Clinic studies (e.g., HIC#2000029552) will have completed this screening process as part of that study, and be invited by study staff to participate in this study.

HC subjects. Subjects that have participated in $[^{18}\text{F}]$ FPEB PET as part of other Yale approved protocols (HIC#1101007933, HIC#1111009365, HIC#2000027842/2000020186) will be contacted by research staff to

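### Scans meant for 2-5 days of abstinence are timed from admission, and no rule sets a tight upper limit on time since last cocaine use; the scan-day and Aim 5 rescan ranges also need harmonising

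*Combined protocol and SAP*

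**What the plan says.** **Stage under study.** Section I, 1 (Statement of Purpose) sets out to study "glutamatergic plasticity and functional brain networks during initial (2-5 days) abstinence".

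**Scan timing.** Every scan rule counts from admission.
- Section I, 4a: "Following admission (approximately 2-5 days), subjects will undergo a single" PET scan, plus an fMRI session.
- Section I, 4c, on repeating a failed PET scan: "if possible within the 2-5 day window following inpatient admission".
- Section I, 4e, first statement: "PET and MRI scanning (between day 3 and day 10; depending on scanner availability", with admission defined as day 1.
- Section I, 4e, next sentence: "CNRU admission will be scheduled at least 1 day (and no more than 5 days) prior to PET/MRI scanning".

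Section 4e applies the same timeline to CUD subjects recruited from other cocaine studies.

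**Recency of use.** Section I, 6 describes the sample: "CUD subjects will be 20 experienced, currently-using, non-treatment-seeking". Section I, 8 requires "Positive urine toxicology screen for cocaine". Section I, 9 places "a urine test to detect cocaine and its metabolites" in the screening work-up. Section I, 4b allows up to a month between screening and the study visits and expects about a week in most cases. It also describes a locked unit with urine testing three times a week. A day-by-day Substance Use Calendar is taken at screening and updated at admission (4b, item iii).

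**Analysis.** Section I, 13 names no variable for days since last use. Its possible covariates are given as examples only. Section IV, item 1 allows intervals between dated procedures to be analysed, but does not mention last use.

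**Aim 5 rescan.** Section I, 1 says within three weeks, typically 5-14 days. Section I, 4f says within one month, typically 10-20 days.

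**The concern.** Days since admission and days of abstinence are the same only if last use fell on the day of admission. The plan defines its scientific stage on one clock and schedules on the other, and nothing converts between them. A scan can therefore obey the admission rule and still lie outside the stated stage.

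This matters because the plan itself proposes that the primary PET outcome moves over this period. The Background (Section I, 3) reports lower mGluR5 availability with longer abstinence, and Aim 5 hypothesises widespread within-person decreases from initial abstinence. If that is right, the Aim 1 comparison of CUD subjects with healthy comparison (HC) subjects could mix abstinence stage with the CUD effect. Later scans would work against the hypothesised striatal increase and towards the hypothesised prefrontal decrease. Without days since last use in the analysis, a reader could not separate the two.

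The Aim 5 pilot is meant to supply effect sizes for further funding. A change estimated over 5-14 days need not match one estimated over 10-20 days, so the interval is part of what is being estimated.

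**Working it through.** The plan gives no figure for this point, so the check is mainly of day counts.

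**1. Scan windows on one clock.** Days after admission = study day minus 1, because admission is day 1.
- Day 3-10: 3 - 1 = 2 to 10 - 1 = 9, so 2-9 days after admission.
- Next sentence of 4e: 1-5 days after admission.
- Days meeting both: 2, 3, 4, 5.
- Days meeting only one: 1, 6, 7, 8, 9.

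The overlap equals the 2-5 days of 4a and 4c.

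**2. From admission to abstinence.** Let L be days from last use to admission (not given, so assumed) and s be days from admission to scan, with no cocaine taken on the unit. Abstinence at scan = L + s. For s of 2-5:

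| L | Abstinence at scan | Scan days (s) within 2-5 days of abstinence |
|---|---|---|
| 0 | 2-5 | 2, 3, 4, 5 |
| 1 | 3-6 | 2, 3, 4 |
| 2 | 4-7 | 2, 3 |
| 3 | 5-8 | 2 |
| 7 | 9-12 | none |

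At the cap, s = 5 and abstinence is 5 + L, which exceeds 5 for any L of 1 or more. For L of 4 or more, even s = 2 gives at least 6 days.

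**3. What bounds L.** The locked unit makes abstinence at least s, a lower bound, for subjects given no laboratory cocaine there. The upper side rests on a positive urine test at screening, followed by up to one month (about a week in most cases) to the study visits. That is a bound, but far wider than 5 days. The calendar would show L, yet no rule refers to it.

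**4. Aim 5.** The typical windows 5-14 and 10-20 share days 10-14, which is 5 of the 16 days they cover together (5-20). The outer limits also differ: 21 days against about a month.

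**5. Precision of the supportive analyses proposed below.** Section 13 gives a PET non-centrality of 3.60, critical t of 1.81 on 38 df and power 0.96. The non-central t at those values gives 0.961, which reproduces it. I use two-sided alpha 0.05 (critical t 2.024), where 20 + 20 subjects give 0.94. The implied effect is d = 3.60/sqrt(10) = 1.14.

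*Comparison limited to n CUD scans at 2-5 days since last use, against 20 HC.* Non-centrality = 1.14 x sqrt(20n/(n + 20)), using the unrounded d.
- n = 20: 3.60, power 0.94.
- n = 15: 3.33, power 0.90.
- n = 10: 2.94, power 0.81.

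*CUD-HC difference at 3.5 days* (covariate is days minus 3.5 in CUD, 0 in HC). Variance factor = 1/20 + 1/20 + (mean - 3.5)²/SS. I assume 20 CUD scans spread evenly over four days, so SS = 5 x (2.25 + 0.25 + 0.25 + 2.25) = 25, with no drop in residual variance.
- Mean 3.5: 0.10, SE x1.00, power 0.94.
- Mean 4.5: 0.10 + 1/25 = 0.14, SE x sqrt(1.4) = 1.18, power 0.84.
- Mean 5.5: 0.10 + 4/25 = 0.26, SE x sqrt(2.6) = 1.61, power 0.58. These scans run from day 4 to day 7, so 3.5 lies outside the data.

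**The case against.** The strongest reply is that the two statements in 4e sit side by side and can both be obeyed. Day 3-10 can be read as a calendar envelope that depends on the scanner, with the 5-day cap as the specific limit. Together they give exactly the 2-5 days of 4a and 4c. This stands. A reader might infer two irreconcilable scan rules, or that the plan endorses scans 9 days after admission; the text supports neither. What remains is a conflict at the edges that lets someone scheduling a scan cite the plan either way.

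A reader might also infer that time since last use is not bounded at all. It is, loosely: from below by the locked unit, and from above by the positive screen and the limit on the interval to study visits. Subjects are current users not seeking treatment, and nothing in the documents suggests that they stop well before admission. With L = 1, scans 2-4 days after admission remain inside the stage. This also stands. What is missing is a tight upper limit, and the overrun at the cap needs only one day.

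It is tempting to turn the 60-80% reduction quoted in the Background into a bias per day. The documents do not support that. The result is between-subject, an earlier study found no cocaine-related change, and the Background says the within-person course has not been examined directly. Section 13 words the change as suggested by prior research and conditional on being observed; it does not assert it.

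Finally, Aim 5 is an optional pilot of up to 10 CUD subjects, its typical ranges are descriptive, and three weeks lies inside one month. That makes the mismatch minor, but it does not settle which interval is intended.

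**Conclusion.** The point holds in a limited form. The intended window of 2-5 days after admission can be recovered, but the day 3-10 text contradicts it at the edges. Even the recovered window does not deliver 2-5 days of abstinence, because no scan or analysis rule uses time from last use. At the 5-day cap, any gap of 1 day or more between last use and admission takes the scan past the stated stage.

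The consequence for Aim 1 is conditional: it arises only if mGluR5 changes with abstinence over these days and if a material share of CUD subjects have L of 1 or more. The documents establish neither, so I put no size on the bias. For Aim 5, the two typical windows agree on 5 of 16 days.

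This should be fixed, because the data needed are largely collected already and the change is small. Confidence is medium.

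**What to change.** 1. Delete the day 3-10 text in Section I, 4e. State one limit there and in 4a and 4c: scan 2-5 days after admission.
2. Add a scheduling target of 2-5 days since last cocaine use. Make it a target, not an exclusion: with L of 4 or more no scan day meets both, and an arm of 20 should not lose subjects for that.
3. For every CUD subject, derive days from last use to PET and to MRI, including repeat scans. Take last use from the calendar updated at admission, or from the last laboratory cocaine session where there was one.
4. Keep the planned CUD-HC comparison as primary. Add two supportive analyses to Section 13: the comparison limited to CUD scans at 2-5 days since last use, and the CUD-HC difference at 3.5 days. The second assumes a linear slope and should be read only if 3.5 lies within the observed days. Centring the covariate at the CUD mean will not do instead: it makes the covariate orthogonal to group and leaves the group estimate unchanged.
5. State one Aim 5 rescan window in Section I, 1 and 4f. For example, 10-20 days fits both outer limits. Use actual days between scans in the pilot analysis.

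**Cost.** Scheduling around the scanner becomes slightly tighter: for L of 0, 1, 2 or 3 the target leaves 4, 3, 2 or 1 scan days. Last use before admission is self-reported, unlike the admission date. The supportive analyses lose precision if scans run late, as the working shows, which is why they should not replace the primary comparison. The sample size is unchanged.
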